### **2.3. Hypotheses**

#### **Primary hypotheses:**

1. The Test eye drops will be non-inferior to the Control eye drops with respect to change in ocular comfort from baseline at 30-Day follow-up. A non-inferiority margin of -20 point ocular comfort VAS scale will be used.

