#### **14.5. Primary Analysis**

##### **Ocular Comfort (VAS) Score:**

Ocular comfort scores will be analyzed using a linear mixed model for repeated measures to test for the difference between the Test and Control eye drops. The regression model will include treatment group (Test, Control), time (0, 7-Day and 30-Day) and group by time interaction as fixed effect factors; and investigational site as random effect. Age and gender will be included in the model when appropriate. The correlation between measurements from the same subject across time will be modeled using unstructured (UN) variance-covariance matrix. If the estimation algorithm does not converge, then a Compound Symmetry matrix (CS) will be used. The log-likelihood ratio test will be used to test for the

homogeneity between the residual covariance structures across treatment groups. The Kenward and Roger method will be used to calculate the denominator degree of freedom.

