#### **Hypothesis Testing:**

The null and alternative hypotheses for non-inferiority of Test relative to Control are as follows:

$$H_0: \Delta \leq -20$$
$$H_A: \Delta > -20,$$

where  $\Delta$  is the difference between treatment groups in mean change from baseline at 30-Day follow-up (Test minus Control). The non-inferiority test will be based on the least square mean change difference and corresponding 95% confidence interval from the final model. The lower bound of the 95% confidence interval will be compared to the non-inferiority margin of -20. If the lower bound is greater than -20, the null hypothesis will be rejected, and the Test will be considered non-inferior to Control. The primary analysis will be conducted on the Per-Protocol Population. As sensitivity analysis will be conducted on the ITT Population.

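### If the unstructured matrix fails to converge, the compound-symmetry fallback can misstate the standard error of the Day 0 to Day 30 change, in either direction

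*Combined protocol and SAP*

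**What the plan says.** Section 14.5 (Primary Analysis, Ocular Comfort) treats the baseline score as one of three repeated outcomes. The fixed effects are treatment, "time (0, 7-Day and 30-Day) and group by time interaction as fixed effect factors", and site is a random effect. On covariance it says: "The correlation between measurements from the same subject across time will be modeled using unstructured (UN) variance-covariance matrix". The next sentence gives the only alternative: "If the estimation algorithm does not converge, then a Compound Symmetry matrix (CS) will be used". No intermediate structure, change of optimiser or robust variance is mentioned.

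Two other provisions concern the covariance. A likelihood-ratio test examines "homogeneity between the residual covariance structures across treatment groups", and the Kenward-Roger method "will be used to calculate the denominator degree of freedom".

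The estimand under Hypothesis Testing is the Test minus Control difference in mean change from baseline to Day 30, taken from the final model. The decision rule is: "The lower bound of the 95% confidence interval will be compared to the non-inferiority margin of -20". The primary population is Per-Protocol, which under Section 14.3 requires all visits to be completed. Section 14.6 reuses the same model for quality of vision. Section 14.1 leaves further detail to a stand-alone SAP that is not among the documents reviewed.

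**The concern.** Compound symmetry imposes one variance and one correlation on all visits. The primary contrast uses only Days 0 and 30, so its standard error should reflect the variance of that particular change. Under compound symmetry it reflects an average in which the Day 0 to 7 and Day 7 to 30 changes count equally.

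The other provisions do not help. Kenward-Roger adjusts within the assumed structure and does not repair a wrong one. The homogeneity test compares arms, not visits. If the fallback were used and the structure were wrong, the lower bound set against -20 would be misplaced: too high (excess false non-inferiority claims) or too low (lost power). This is the single primary analysis of a study meant to support European registration.

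**Working it through.** **Inputs.** From Section 14.2: SD of the change 35, 56 completers per arm, two-sided alpha 0.05, power at least 85%. From Sections 2.3 and 14.5: margin -20. Visit-specific variances and correlations are not in the documents and are assumed below.

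**1. The plan's own figure.** Reading the stated difference of 20 as the margin, with a true difference of 0, the normal approximation is n = 2 × 35² × (1.960 + 1.036)² / 20² = 55 per arm. The noncentral t calculation gives 84.4% power at 55 and 85.0% at 56. The planned 56 per arm reproduces, at a one-sided level of 0.025.

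**2. Correct interval.** SE = 35 × √(2/56) = 6.61. The half-width is 1.982 × 6.61 = 13.1 (t, 110 df).

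**3. What compound symmetry estimates.** With complete balanced data:

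- true variance of the change = V(0) + V(30) − 2·Cov(0,30);
- compound-symmetry value = 2 × (mean of the three variances − mean of the three covariances), which equals the average of the three pairwise change variances.

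With equal variances, the SE ratio is k = √[(1 − mean r) / (1 − r(0,30))]. One-sided error at a true difference of -20 is 1 − Φ(1.96k). Power at a true difference of 0 is 1 − Φ(1.971k − 20/6.61), where 1.971 is the t quantile on 220 df, also used for the half-widths.

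**4. Examples.** For correlations (0-7, 0-30, 7-30) of (.3, .3, .7), mean r = 0.433 and k = √(0.567/0.7) = 0.90. For (.5, .3, .7), k = √(0.5/0.7) = 0.845. For (.5, .6, .4), k = √(0.5/0.4) = 1.118. With all correlations .5 and a Day 7 SD 30% larger, the mean variance is (1 + 1.69 + 1)/3 = 1.23 and the mean covariance (0.65 + 0.5 + 0.65)/3 = 0.60. Then k = √[2 × (1.23 − 0.60) / 1] = 1.12.

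| Assumed pattern | k | Half-width | One-sided error | Power |
|---|---|---|---|---|
| (.5, .5, .5) | 1.00 | 13.0 | 2.5% | 85% |
| (.6, .5, .4) | 1.00 | 13.0 | 2.5% | 85% |
| (.5, .5, .6) | 0.97 | 12.6 | 2.9% | 87% |
| (.3, .3, .7) | 0.90 | 11.7 | 3.9% | 89% |
| (.5, .3, .7) | 0.845 | 11.0 | 4.9% | 91% |
| (.5, .6, .4) | 1.118 | 14.6 | 1.4% | 79% |
| .5 throughout, Day 7 SD 30% larger | 1.12 | 14.6 | 1.4% | 79% |

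The apparent power gains in the narrow-interval rows only reflect the inflated error.

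**5. Simulation.** With 40,000 trials per pattern, and without site, age or gender, compound symmetry gave one-sided errors of 2.5% (.5, .5, .5), 3.8% (.3, .3, .7), 4.9% (.5, .3, .7) and 1.5% (.5, .6, .4). Analysing the Day 0 to Day 30 change directly gave 2.4 to 2.6% throughout.

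**6. The replacement.** The large-sample fit of heterogeneous Toeplitz was computed for these patterns and others, including ones that break its equal lag-1 assumption. The SE ratio was 0.99 to 1.01 and one-sided error 2.4 to 2.6%.

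**The case against.** **The trigger is rare.** An unstructured matrix on three visits has 6 parameters, estimated from about 112 subjects who by definition completed every visit. It should nearly always converge. Separate matrices by arm would need 12 parameters, but 56 complete subjects per arm still determine each matrix well. The random site term adds some risk. This objection stands and limits the point's importance. As an illustration, if the matrix failed in 1 to 10% of trials (assumed), overall one-sided error would be between 2.5 + 0.01 × (3.9 − 2.5) = 2.51% and 2.5 + 0.10 × (4.9 − 2.5) = 2.74%, even under the unfavourable patterns.

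**The direction is not known.** A reader might infer that the fallback necessarily narrows the interval, because Days 7 and 30 are on treatment and baseline is not. Section 7.2 lends this some plausibility: the baseline score precedes the first study drop, and at Visits 2 and 3 subjects should already have used the drop at least twice that day. But Section 3.2 admits current users of artificial tears, and the Visit 1 steps include no washout of habitual tears before the baseline score. Baseline is therefore not reliably an untreated state, and no correlations are given. The stronger reading is not supported.

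**The effect is small in points.** Under (.3, .3, .7) the half-width falls from 13.1 to 11.7. The decision changes only for observed differences between about -8.3 and -6.9. This also stands.

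**A rule already exists, and the stand-alone SAP may refine it.** True, but Section 14.5 already commits to compound symmetry. Choosing another structure after seeing a failure would be a data-dependent choice.

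**Conclusion.** The point holds conditionally. If the unstructured matrix fails, compound symmetry gives the primary contrast the average change variance of the three visit pairs. This is correct only when the Day 0 to Day 30 change has that average variance. Over the assumed patterns, one-sided error ranges from 1.4 to 4.9% against 2.5%, and power can drop to about 79%. Neither Kenward-Roger nor the between-arm homogeneity test would correct or reveal this.

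The documents do not support saying that the non-inferiority error rate is lost, or that the bias favours Test. Both would need correlations that the plan does not report and a convergence failure that is unlikely. The figures also assume complete data and leave out site, age and gender. This is a cheap improvement to a stated rule and does not threaten the design.

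**What to change.** In Section 14.5, or in the stand-alone SAP before database lock, replace the direct step to compound symmetry with an ordered rule. If the unstructured matrix does not converge, fit heterogeneous Toeplitz, whose lag-2 correlation is exactly the Day 0 to Day 30 one. If that also fails, analyse the Day 30 change in the Per-Protocol Population by ANCOVA with treatment, baseline and site, which needs no covariance structure across visits. State that the same rule applies to quality of vision, since Section 14.6 borrows this model.

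The cost is a sentence or two and one more pre-specified step; 56 per arm is unchanged. There are two limitations. Heterogeneous Toeplitz has 5 parameters, only one fewer than unstructured, so it may fail for the same reason; the ANCOVA step is there for that case. In the ITT sensitivity analysis, ANCOVA would drop subjects without a Day 30 score, so there it should be paired with the multiple imputation already planned in Section 14.9.

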#### **Hypothesis Testing:**

The null and alternative hypotheses for non-inferiority of Test relative to Control are as follows:

$$H_0: \Delta \leq -20$$
$$H_A: \Delta > -20,$$

where  $\Delta$  is the difference between treatment groups in mean change from baseline at 30-Day follow-up (Test minus Control). The non-inferiority test will be based on the least square mean change difference and corresponding 95% confidence interval from the final model. The lower bound of the 95% confidence interval will be compared to the non-inferiority margin of -20. If the lower bound is greater than -20, the null hypothesis will be rejected, and the Test will be considered non-inferior to Control. The primary analysis will be conducted on the Per-Protocol Population. As sensitivity analysis will be conducted on the ITT Population.

#### **14.6. Secondary Analysis**

##### Corneal Staining (Grade 2 or higher):

Corneal staining response using FDA grading scale (i.e. Grade 0 = None, Grade 1 = Trace, Grade 2 = Mild, Grade 3 = Moderate and Grade 4 = Severe) will be first categorized into a binary outcome as 1 if any grade 2 or higher corneal staining otherwise 0. Events occurring during an unscheduled visit will be counted in the subsequent visit. For example, if a Grade 2 corneal staining was reported at an unscheduled visit between Visit 1 and Visit 2, it would be counted in Visit 2. Eyes with multiple reports will be counted only once at each visit for the analysis purpose. The binary outcome will be then analyzed using a generalized linear mixed model for binary data. The regression model will include treatment group (Test, Control), time (0, 7-Day and 30-Day) and group by time interaction as fixed effect factors; and investigational site and subject as random effects (G-side). Baseline values, age and gender will be included in the model as fixed covariates when appropriate. The correlation between measurements from the same subject/eye across time will be modeled using UN variance-covariance matrix (R-side). If the estimation algorithm does not converge, then a compound symmetry structure (CS) will be used. The Kenward and Roger method will be used to calculate the denominator degree of freedom.

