#### **Secondary hypotheses:**

1. The proportion of eyes with Grade 2 or higher corneal staining in the Test group will be no different to that in the Control group.
2. The change in overall quality of vision from baseline at 7-Day and 30-Day follow-up of the Test eye drops will be no different to that of the Control eye drops.
3. The proportion of eyes with reported ocular symptoms in the Test group will be no different to that in the Control group.
4. The Test eye drops will be non-inferior to the Control eye drops with respect to change in ocular comfort from baseline at 7-Day follow-up. A non-inferiority margin of -20 point ocular comfort VAS scale will be used.

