### **3.3. Exclusion Criteria**

Potential subjects who meet any of the following criteria will be excluded from participating in the study:

1. Currently pregnant or breast-feeding.
2. Diabetes.
3. Any ocular or systemic allergies or disease which may interfere with the clinical trial (at the investigator's discretion).
4. Any systemic disease, autoimmune disease, or use of medication which may interfere with the clinical trial (at the investigator's discretion).
5. Any infectious diseases (e.g. hepatitis, tuberculosis) or a contagious immunosuppressive disease (e.g. HIV), by self-report.
6. Any Grade 3 or greater biomicroscopy findings (this includes, corneal edema, corneal staining, corneal vascularization, conjunctival injection, tarsal abnormalities, bulbar injection) on the FDA scale.
7. Any active ocular abnormalities/conditions that may interfere with the clinical trial (this includes, but not limited to, chalazia, recurrent styles, pterygium, infection, etc.).
8. Any corneal distortion due to previous rigid gas permeable lens wear, surgery or pathology.
9. History of any ocular or corneal surgery (e.g. RK, PRK, LASIK).
10. Participation in any pharmaceutical or medical device related clinical trial within 30 days prior to study enrollment.
11. History of binocular vision abnormality or strabismus.
12. Habitual wearers of soft contact lenses in the past 1 month or rigid gas permeable lens within the past 3 months.
13. Current habitual use of Prescription Medicines to treat dry eye or ocular discomfort, ocular steroids, or any medication (RX or OTC) that would interfere with the clinical study (at the discretion of the investigator).
14. Employees of investigational clinic (investigator, coordinator, and technician, etc.) or family member of an employee of the clinical site by self-report.

In addition to the above criteria, patients with any allergy or sensitivity to ingredients that this product may contain (Castor Oil, Polyoxy 40 Hydrogenated Castor Oil, Sodium Chlorite, Boric Acid, Sodium Borate Decahydrate, Sodium Chloride, Potassium Chloride, Calcium Chloride Dihydrate, Magnesium Chloride Hexahydrate, Polyethylene Glycol 400, Sodium Hyaluronate, Purified Water) should not participate in the study.

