## 7.2. Detailed Study Procedures

### VISIT 1

Aim for Visit 1 to occur in the afternoon (after 12 PM). The subjects must present to Visit 1 wearing their spectacles (if applicable). Subjects will be asked to bring their habitual artificial tears with them to the visit (if applicable).

Visit 1: Screening		
Step	Procedure	Details
1.1	Statement of Informed Consent	Each subject must read, understand, and sign the Statement of Informed Consent and Privacy Statement before being enrolled into the study. The Principal Investigator or their designee conducting the informed consent discussion must also sign the consent form.  Note: The subject must be provided a signed copy of this document.
1.2	Demographics	Record the subject's date of birth, gender, race and ethnicity.
1.3	Medical History and Concomitant Medications	Questions regarding the subjects' medical history and concomitant medications.
1.4	Artificial Tear Use	The subject will be asked about their artificial tear use.
1.5	Eligibility after Screening	All responses to Screening Inclusion Criteria questions must be answered "yes" and all responses to Exclusion Criteria must be answered "no" for the subject to be considered eligible.

Visit 1: Baseline		
Step	Procedure	Details
1.6	Entrance Visual Acuity	Record the distance high contrast visual acuity to the nearest letter (OD, OS, and OU) with their habitual spectacle correction in place (or unaided if applicable).
1.7	Baseline SROS	Subjects will respond to a verbal open-ended symptoms questionnaire.
1.8	Baseline VAS	The subject will respond to the VAS questionnaire
1.9	Baseline PRO questionnaires	The subject will complete the electronic questionnaires using the Kiosk portal.
1.10	Tear break-up time	Record the tear film stability (NITBUT), OD and OS, with a Medmont or other topographer.

Visit 1: Baseline			
Step	Procedure	Details	
1.11	Slit Lamp Biomicroscopy	
The FDA slit lamp classification scale will be used to grade the findings and determine eligibility.
 
If there are any Grade 3 or higher other slit-lamp findings, the subject is ineligible to continue at this time, but may return up to one additional time to determine eligibility. If discontinued a final examination must be completed.
 
If there are no slit lamp findings, and the clearance of the fluorescein needs to be expedited, preservative-free rewetting drops or saline may be instilled.
	

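### The corneal-staining endpoint counts staining carried in from Visit 1 and cannot register worsening from Grade 2 to Grade 3 or 4; section 14 plans no between-arm analysis of change in grade

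*Combined protocol and SAP*

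**What the plan says.** **Entry.** Section 3.3, item 6, excludes "Any Grade 3 or greater biomicroscopy findings (this includes, corneal edema, corneal staining" and other slit lamp signs. Step 1.11 of section 7.2 uses the same threshold: "If there are any Grade 3 or higher other slit-lamp findings, the subject is ineligible to continue at this time". Grade 2 staining at Visit 1 is therefore compatible with enrolment.

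**Endpoint.** Section 14.6 sets out the scale as "Grade 0 = None, Grade 1 = Trace, Grade 2 = Mild, Grade 3 = Moderate and Grade 4 = Severe". Staining "will be first categorized into a binary outcome as 1 if any grade 2 or higher corneal staining otherwise 0". Secondary hypothesis 1 in section 2.3 matches this: "The proportion of eyes with Grade 2 or higher corneal staining in the Test group will be no different" from that in the Control group.

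**Model.** The binary outcome goes into a generalized linear mixed model in which time has three levels (Day 0, Day 7 and Day 30), with a group-by-time term. On adjustment: "Baseline values, age and gender will be included in the model as fixed covariates when appropriate". No rule says when it is appropriate. The odds ratio is tested at each follow-up visit and also over all visits together, in the Safety Population.

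**Other capture of grades.** Slit lamp findings on the FDA scale are listed under other endpoints (section 2.2). Section 13.1 treats worsening of a pre-existing condition as an adverse event and lists Grade 3 or higher corneal findings among significant ocular events. Section 14.1 promises summary tables for safety variables. Section 14.7 plans no exploratory analyses.

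**The concern.** The entry limit and the event threshold overlap at Grade 2. In people recruited for dryness symptoms or artificial tear use, some eyes may already be at Grade 2 before the first drop. Two consequences follow.

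- **Dilution.** An eye at Grade 2 on Day 0 and still at Grade 2 on Day 30 is an event, although nothing has changed. Randomization balances such eyes in expectation, so neither arm is favoured, but they pull an unadjusted odds ratio towards 1. The stated hypothesis is no difference, so dilution makes a safety signal easier to miss.
- **Lost worsening.** An eye that goes from Grade 2 to Grade 3 or 4 scores 1 at both times. A covariate cannot recover it, because the outcome has only two levels.

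Safety is a stated objective (section 2.1), and staining is the only slit lamp sign for which section 14 plans a between-arm test. Comfort and quality of vision, by contrast, are defined as change from baseline.

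**Working it through.** **The plan's own figure.** Section 14.2 gives 56 per arm. That reproduces for the comfort endpoint (difference 20, SD 35, two-sided 0.05, power 85%: 55 by normal approximation; 56 with the t-test, power 85.0%). It says nothing about staining, for which the documents give no expected rate, power or sample size. From the documents I take only 60 randomized per arm and the two-sided 5% level. All staining rates below are assumptions.

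**1. Worsening.** Let *b* be the proportion at Grade 2 on entry. Suppose all of these stay at Grade 2 or higher, new onset is 5% in both arms, and Grade 2 entrants worsen to Grade 3 or higher in 30% (Test) v 5% (Control).

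- Endpoint, either arm: *b* + (1 − *b*) × 0.05. At *b* = 10%: 0.10 + 0.90 × 0.05 = 14.5%. At *b* = 20%: 0.20 + 0.80 × 0.05 = 24%. The odds ratio is 1 in both cases.
- Worsened subjects per 60 at *b* = 10%: 60 × 0.10 × 0.30 = 1.8 (Test) v 60 × 0.10 × 0.05 = 0.3 (Control).
- At *b* = 20%: 3.6 v 0.6.

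The numbers are small, but the endpoint is the same in both arms whatever the excess of worsening.

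**2. Dilution.** One eye per subject and one follow-up visit. New Grade 2+ among those entering below Grade 2 is *r* = 15% (Test) v 3% (Control). Entry Grade 2 persists with probability *q*, equal in both arms.

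Observed proportion = *bq* + (1 − *b*)*r*.

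| *q* | *b* | Test | Control | Unadjusted OR |
|---|---|---|---|---|
| any | 0 | 0.15 | 0.03 | 5.7 |
| 1 | 10% | 0.10 + 0.135 = 0.235 | 0.10 + 0.027 = 0.127 | 2.1 |
| 1 | 20% | 0.20 + 0.12 = 0.32 | 0.20 + 0.024 = 0.224 | 1.6 |
| 0.5 | 10% | 0.05 + 0.135 = 0.185 | 0.05 + 0.027 = 0.077 | 2.7 |
| 0.5 | 20% | 0.10 + 0.12 = 0.22 | 0.10 + 0.024 = 0.124 | 2.0 |

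**3. What adjustment recovers.** The same scenario, simulated under three analyses: unadjusted, stratified by Visit 1 status (Mantel-Haenszel), and a treatment-emergent event. No Grade 2 entrant is assumed to worsen, so the treatment-emergent proportions are (1 − *b*)*r*: 13.5% v 2.7% at *b* = 10%, and 12% v 2.4% at *b* = 20%.

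| Persistence | *b* | Unadjusted | Baseline-adjusted | Treatment-emergent |
|---|---|---|---|---|
| 100% | 10% | 33% | 61% | 61% |
| 100% | 20% | 21% | 54% | 54% |
| 50% | 10% | 40% | 47% | 61% |
| 50% | 20% | 27% | 34% | 54% |

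Powers are approximate: the normal approximation gives about 58% and 53% where the last column has 61% and 54%. With full persistence, the Grade 2 stratum consists only of events, so stratifying removes it and adjustment does as well as redefinition. With partial persistence, that stratum adds variation unrelated to new staining, and adjustment recovers only part of the loss.

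**The case against.** The other side has a good deal to say.

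- **The trial does record worsening.** A reader might infer that a move from Grade 2 to Grade 3 or 4 would leave no trace. The documents do not support that. Eyes are graded at every visit, slit lamp findings are a listed endpoint, worsening of a pre-existing condition is an adverse event, and Grade 3 or higher corneal findings are significant events. Summary tables by category also fall within section 14.1. What is missing is a planned between-arm analysis of change in grade.
- **Baseline adjustment is provided for.** A reader might take the unadjusted column (33% and 21%) as the power of the plan. That would be wrong if Visit 1 grade is in the model. The fair criticism is narrower: inclusion is optional and has no rule. If it is used while Day 0 is also a response level, baseline is both outcome and covariate.
- **Prevalence at follow-up is a valid randomized comparison**, and it is the hypothesis section 2.3 states. This stands. Treatment-emergent staining is a different estimand, which is a reason to add it and not to replace the existing one.
- **The rates are invented, and the model is simpler than the plan's**, which uses both eyes, repeated visits and random effects. This also stands. If Grade 2 at entry is rare, dilution is negligible.
- **Section 14.1 defers detail to a stand-alone SAP**, which may settle some of this. It is not among the documents reviewed, and section 14 as written does not.

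**Conclusion.** The point holds in a limited form. By the plan's own definitions, Grade 2 is allowed at entry, persistent Grade 2 counts as an event in both arms, and worsening from Grade 2 to 3 or 4 cannot change the outcome. That last statement needs no assumed rate and holds with or without adjustment.

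The size of the dilution is uncertain. It depends on the prevalence and persistence of Grade 2 at entry, which the documents do not give, and on whether baseline is adjusted for. In the illustration, the treatment-emergent analysis gains nothing over baseline adjustment at full persistence, and gains about 14 points (61 − 47) to 20 points (54 − 34) at 50% persistence.

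The documents do not support the stronger readings that the trial would fail to record such harm, that one arm is favoured, or that the prevalence comparison is invalid. This is an inexpensive improvement to a secondary safety analysis, with no bearing on the primary endpoint.

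**What to change.** In section 14.6, and in the stand-alone SAP before database lock:

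1. **Add** a between-arm comparison, at Day 7 and Day 30, of treatment-emergent staining: Grade 2 or higher and at least one grade above that eye's own Visit 1 FDA grade (step 1.11). Visit 1 serves as reference only.
2. **Keep** the Grade 2+ prevalence comparison, but adjust for Visit 1 grade unconditionally, model only the follow-up visits as responses, and restrict the pooled comparison to visits after treatment has started.
3. **Add** a table by arm of the shift from Visit 1 grade to worst follow-up grade.

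The cost is wording and programming; the FDA grades are already collected at each visit. There are two drawbacks. Treatment-emergent events will be few, so the interval for the odds ratio may be wide. The new measure also gives no credit for improvement in eyes stained at entry, which is why the prevalence comparison should stay.

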#### **Hypothesis Testing:**

The null and alternative hypotheses for no difference of Test relative to Control are as follows:

$$H_0: OR = 1$$
$$H_A: OR \neq 1,$$

where  $OR$  is odds ratio of having a Grade 2 or higher corneal staining in the Test group over the Control group.

Comparison between the Test and Control will be conducted at each follow-up visit and across all visits. The test for no difference will be based on the estimated OR and corresponding 95% confidence interval from the final model. The null hypothesis will be rejected in favor of the alternative if 1 does not fall within the 95% confidence interval of OR. The corneal staining analysis will be conducted on the Safety Population.

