**Subject reported Ocular symptoms (yes/No)**

Reported ocular symptoms, problems or complaints (0 = No, 1 = Yes) at any visit will be analyzed using the same method described above for corneal staining. The reported ocular analysis will be conducted on the Safety Population.

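### Section 14.6 lets the baseline value be both a response and a covariate in the staining and symptom models; when both are used, the follow-up odds ratios are noisier and their 95% intervals too narrow

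*Combined protocol and SAP*

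**What the plan says.** Section 14.6, Corneal Staining, specifies a generalized linear mixed model for a binary outcome. Its fixed effects are treatment group, "time (0, 7-Day and 30-Day) and group by time interaction as fixed effect factors", so the Visit 1 result is one of the modelled responses. It takes "investigational site and subject as random effects (G-side") and adds an R-side covariance matrix. The next sentence reads: "Baseline values, age and gender will be included in the model as fixed covariates when appropriate". The text gives no criterion for that qualifier. It does not drop the time-0 rows when the covariate enters, and it does not let the covariate's effect differ by visit.

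Under Hypothesis Testing in the same section: "Comparison between the Test and Control will be conducted at each follow-up visit and across all visits". Whether time 0 counts among all visits is not stated. The decision rule is: "The null hypothesis will be rejected in favor of the alternative if 1 does not fall within the 95% confidence interval of OR".

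Reported ocular symptoms "will be analyzed using the same method described above for corneal staining", so two secondary endpoints are involved. The primary comfort model in Section 14.5 also has time 0 as a response but lists no baseline covariate ("Age and gender will be included in the model when appropriate"). Quality of vision follows that primary model. Neither has the conflict.

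**The concern.** A baseline measurement can be handled in two coherent ways in a longitudinal model. It can be the first response, or it can be a covariate for the later responses. Section 14.6 permits both at once. On a time-0 row the covariate then is the response. Those rows carry no information about treatment, yet they help to estimate the one baseline coefficient that is applied to Day 7 and Day 30.

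Baseline positives can occur. Exclusion criterion 6 removes only "Any Grade 3 or greater biomicroscopy findings", so Grade 2 staining may be present at entry, and symptoms are recorded at Visit 1 before the first drop (Section 7.2, step 1.7).

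At stake are the size, precision and error rate of the odds ratios for two secondary endpoints, both analysed on the Safety Population. The qualifier also leaves the analyst to choose, without a rule, between a coherent model and a mis-specified one.

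**Working it through.** **Plan's own figure.** The plan states no rate, power or precision for staining or symptoms. Its only computed figure is 56 per arm for the primary endpoint. With margin 20, SD 35, true difference 0 and two-sided 0.05, the noncentral t gives 85.02% power at 56 and 84.4% at 55. The figure reproduces and is not affected by this point.

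**Mechanism.** For subject i, eye j, visit t, with baseline value b:

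logit P(y_ijt = 1) = group × time terms + β·b_ij + u_i, where u_i has SD σ_u.

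At t = 0, y_ij0 = b_ij. Those rows alone would push β without limit, while the Day-7 and Day-30 rows support a finite β. The common β settles in between and is too large for follow-up. The inflated β·b term also absorbs between-subject variation, so σ_u is underestimated. Test versus Control is a between-subject comparison, so a σ_u that is too small gives a standard error that is too small.

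**Simulation inputs.** 60 subjects per arm (Section 4.3), two eyes, visits 0, 7 and 30 (Section 14.6). Assumed, because the documents give no rates: logit intercept −1.5 or −2.5, subject SD 1.5 or 2.5, eye SD 0.5–0.7, follow-up log OR 0 or 0.8. Model A has responses at 0, 7 and 30 plus the baseline covariate. Model B has responses at 7 and 30 plus the baseline covariate. Both are random-intercept logistic fits.

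**Results for intercept −1.5, subject SD 1.5, eye SD 0.7, 600 runs, Day 30:**

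| True log OR | Model | Mean log OR | Sampling SD | Mean reported SE | 1 outside 95% CI |
|---|---|---|---|---|---|
| 0 | A | −0.011 | 0.421 | 0.379 | 8.2% |
| 0 | B | −0.011 | 0.383 | 0.403 | 3.7% |
| 0.8 | A | 0.815 (OR 2.26) | 0.415 | 0.372 | 57.2% |
| 0.8 | B | 0.729 (OR 2.07) | 0.382 | 0.398 | 43.7% |

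- Noise: 0.421/0.383 = 1.10 and 0.415/0.382 = 1.09.
- Standard error: 0.379/0.421 = 0.90. A normal approximation then predicts rejection of a true null at 2 × [1 − Φ(1.96 × 0.90)], about 8%, which matches 8.2%. The Monte Carlo error around 5% is √(0.05 × 0.95/600) = 0.9 points.
- Average of Days 7 and 30 under no effect: 1 is excluded in 10.0% of runs (A) against 4.8% (B).
- Size with an effect: 0.815/0.729 = 1.12.
- All visits including time 0, true log OR 0.8: A averages 0.549 (OR 1.73), against 0.742 (OR 2.10) for B over Days 7 and 30. 0.549/0.742 = 0.74, so about 25% nearer the null. The cause is dilution: 3 × 0.549 − 2 × 0.829 = −0.011, where 0.829 is A's average over Days 7 and 30, so the time-0 contrast is essentially zero. Under no effect this average excluded 1 in 4.8% of runs.

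**Across scenarios.** Over six scenarios of 300 runs plus the 600-run sets, β rose from about 1.4–1.5 to 2.7–2.9 (2.2 to 3.4 with subject SD 2.5). Estimated σ_u fell from about 1.1 to 0.6–0.7 (1.5 to about 1.0). The sampling SD was 6–10% larger, and 1 was excluded in 7–10% of null runs against 3–5%. A separate two-eye simulation with 300 runs per scenario gave β 1.4 to 2.7, SD 10–13% larger, reported SE 0.37–0.38 against an actual 0.43–0.44, and 8–10% against 4–6%. A smaller set (150 runs each, assumed baseline rates 26%, 10% and 5%, log OR 0.8) gave Day-30 means of 0.84, 0.86 and 0.91 for A against 0.77, 0.79 and 0.82 for B, with SD up about 5–9%.

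**The case against.** The double use is conditional. The plan does not commit the sponsor to it, and Section 14.1 defers detail to a stand-alone SAP to be signed before database lock. That is fair, but nothing in the available text says when the covariate enters or removes time 0 when it does.

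The shift in the estimate is small beside the noise: 0.07–0.09 on the log scale against sampling SDs of 0.40–0.83 in the 150-run set. This stands, and it is why the error rate and standard error matter more than the size of the estimate.

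Some stronger readings are tempting and are not supported:

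- *The odds ratio is exaggerated throughout.* There is no bias at an odds ratio of 1, and an all-visits odds ratio that includes time 0 moves the other way. Model A's 0.815 is also close to the assumed subject-level value of 0.8. The excess is relative to the baseline-adjusted odds ratio, which is a different quantity.
- *The effect is large, intervals are too wide and the error rate holds.* A marginal model (exchangeable GEE with robust standard errors) gives a Day-30 log OR 33% larger, an SD 28–29% larger and about 5% rejection under no effect. Section 14.6 specifies a subject random effect instead, and in that closer model the interval is too narrow.
- *Omitting the covariate is a second fault.* It is not. In a randomized trial an odds ratio without a baseline covariate is valid, and the result matches the structure of the primary model.

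**Conclusion.** The point holds as a should-fix. If the baseline clause in Section 14.6 is used, the staining and symptom models are mis-specified. In the random-intercept simulations the baseline coefficient roughly doubles (about 1.4 to 2.7), the Day-30 log odds ratio is about 6–13% noisier, its reported standard error is too small, and the interval rule rejects a true odds ratio of 1 in about 7–10% of runs rather than 5%. With a real effect, the Day-30 log odds ratio is about 10% larger than the properly adjusted one. An all-visits average that includes time 0 is about 25% closer to the null on the log scale.

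These sizes rest on assumed event rates and correlations. Site effects, the unstructured R-side matrix and the Kenward-Roger adjustment were not reproduced, so they are indicative only. The conflict itself follows from the text and needs no assumption. Only two secondary endpoints are affected; the primary non-inferiority analysis, its margin and the sample size are not.

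**What to change.** In Section 14.6 use baseline once, in the same way for staining and symptoms. Either of these removes the conflict:

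1. Model only the 7-Day and 30-Day responses, with time at two levels, and include the Visit 1 value as a prespecified covariate in every fit, without the qualifier. This is the more precise option.
2. Keep time 0 as a response and delete baseline values from the list of covariates.

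Under either option, state that the all-visits comparison covers the 7-Day and 30-Day visits only.

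The cost is a wording change to the protocol or SAP before database lock. No new data, visits or subjects are needed.
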